## **2.0 Background and Significance**

Approximately half a million operations are performed each year in VA hospitals across the country. Veterans undergoing high-risk surgery have a 1 in 5 chance of suffering complications, a 1 in 10 chance of being readmitted to the hospital within 30 days, and a 1 in 50 chance of dying within 30 days. Long-term survival is significantly reduced for those patients who have perioperative complications, even if they survive to leave the hospital.

Low fitness and poor functional status are among the strongest predictors of postsurgical complications. Prehabilitation takes advantage of the weeks leading up to surgery in order to improve fitness, mobility and nutrition in preparation for the upcoming surgical stress. Indeed, prehabilitation has been shown to improve fitness, reduce complications, and improve quality of life in high-risk surgical patients. The most effective prehabilitation programs combine exercise with nutritional support (are multimodal). They provide exercise that is supervised and individualized and ensure that exercise intensity is appropriate and escalated according to improvements in fitness and strength. Most supervised prehabilitation programs are facility-based, with participation limited by travel time, distance, and transportation. Unfortunately, home-based prehabilitation programs have shown small effect sizes and low compliance rates, likely because the intensity required in programs of such short duration is often not achieved with such unsupervised programs.

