The proposed “tele-supervised” exercise program may allow Veterans living in rural areas and lack transportation or are otherwise unable to travel to participate in prehabilitation in preparation for an upcoming high-risk operation. These findings are expected to inform the design of a larger multicenter trial on the effects of multimodal prehabilitation on surgical outcomes and healthcare resource utilization and to foster the widespread adoption of multimodal prehabilitation in preoperative optimization of high-risk patients at the Durham VAHCS and other VA Health Care Systems. It represents an important step towards providing optimal perioperative care for veterans by identifying and improving fitness, physical function, and nutrition before surgery in a manner that is not geographically constrained. These improvements will contribute to the reduction in health care costs due to decreased complications and fewer readmissions following surgery in high-risk patients.

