### **3.0 Design**

The objective of this protocol is to determine the feasibility, acceptability, and safety and estimate the effect size of a multimodal prehabilitation program that incorporates exercise training and nutritional support. The central hypothesis is that a short-duration, individualized multimodal prehabilitation intervention administered prior to high-risk surgery is feasible and safe at a tertiary VA hospital. The intervention will consist of individualized exercise training delivered remotely using VA telehealth technology, combined with nutritional support consisting of tailored nutritional advice, protein supplementation, and multivitamin and vitamin D supplements. Based on local surgical volume, local expertise in the Gerofit and telehealth exercise programs in non-surgical populations, and published participation numbers and attrition rates, we anticipate that 24 patients can be enrolled and safely participate in a home-based telehealth exercise program plus nutritional support. Adherence to the intervention will be encouraged by use of automated text messages.

This is a pilot intervention that combines the most promising elements of prehabilitation along with innovations in telehealth delivery to develop a VA patient-centered multimodal prehabilitation program with the following specific aims:

- To determine the feasibility, acceptability, and safety of a short-term (3-4 week) multimodal prehabilitation intervention followed by a 4-6 week period of rehabilitation in a cohort of veterans undergoing high-risk surgery.
- To estimate the effect size of a multimodal prehabilitation program for important postoperative outcomes (improvements in functional capacity and physical function, anxiety/depression, and quality of life).

While aspects of the intervention are novel and the work exploratory, based on available evidence, we expect the Cohen’s effect sizes for functional capacity and quality of life to be approximately 1.6 and 0.4, respectively.

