## **4.0 Risk/Benefit Assessment**

### **4.1 Risk Assessment**

There are minimal risks associated with the proposed prehabilitation program. Generally, nutrition and exercise are known to improve health. Physical injury or discomfort are potential risks and are inherent in any exercise, rehabilitation or prehabilitation program. Patients invited to participate will be screened by qualified physical therapists as part of the screening evaluation and the inability to complete the physical functional assessment will be cause for exclusion. Also, patients for whom physical activity is inappropriate or cognitive impairment affects their ability to consent for participation or to successfully participate in the exercise program will not be enrolled. The team has extensive experience with tele-exercise therapies, including strategies for optimizing safety during individual, independent, home-based exercise. Examples of home-based exercises include marching in place, standing (potentially supported) while tapping a heel or toes, performing chair stands, and moving a leg or arm against a resistance band. It is entirely self-regulated, and any advancement will be based on self-reported levels of exertion.

Similarly, the nutrition and vitamin supplementation will be closely monitored by nutrition experts and adjusted based on personal telephone check-ins. Patients with advanced kidney disease are excluded from the study and those with renal impairment (KDIGO 3a and 3b) will receive reduced protein supplement in accord with ESPEN and 2012 KDIGO Guidelines. Renal function will be regularly monitored to ensure there is no adverse effect from the nutritional intervention.

Participation in our study poses no additional cost and every effort will be made to preserve the privacy and confidentiality of participants.

The similarity of the study interventions to conditions potentially encountered in daily life coupled with the measures taken to protect participants from adverse impact create a total risk that is minimal. The types of exercise resemble activities of daily living, especially in that they are self-regulated, and no patient will, or could be forced to do something they choose not to do.

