### **4.2 Benefit Assessment**

The benefit of participation in this study is available to both current enrollees and future patients. If a monitored prehabilitation program paired with nutrition support is found to be feasible, acceptable, and safe, and in the future, adequately powered clinical trials found to be effective, significant improvement to perioperative care is possible. Furthermore, the telehealth component of this program would facilitate delivery of prehabilitation to rural populations and those with limited support or access to transportation.

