## **13.0 Data Analysis and Statistical Considerations**

Feasibility will be assessed by calculating the acceptance rate, measured as the number of patients enrolled divided by the number eligible. In addition, we will evaluate veterans' reasons for enrollment or non-enrollment in the program using patient interviews and semi-structured questionnaire (see Appendix 4). No PHI will be recorded in questionnaires obtained from eligible but non-recruited veterans.

Acceptability will be measured by rate of compliance with the exercise/nutrition programs. For the exercise intervention, the percentage of patients completing  $\geq 75\%$  of sessions divided by the number of enrolled patients will be calculated. For the nutritional intervention, compliance will be measured by the percentage of patients with  $\geq 75\%$  adherence to protein intake goal, as assessed using the text message-based nutrition diary, lids returned, and 24-hour recall administered during the weekly telephone call.

Safety will be evaluated by the number of adverse events (significant injury or medical event) during exercise. A significant injury or medical event is defined as an event that causes the participant to seek attention from a health professional or limits their activities of daily living for at least two days.

Effect size will be estimated by comparing physical function before and after the prehabilitation intervention, as measured by the 5RSTS and the 2-minute step tests using Cohen's D. Changes in health-related quality of life (SF-36) and anxiety and depression (HADS) before surgery and at the 6-week and 24-week study periods following surgery will be calculated.

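### Section 13.0 judges safety only by adverse events during exercise, although Aim 1 asks about the safety of the combined exercise and nutrition program

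*Combined protocol and SAP*

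**What the plan says.** Section 3.0 sets Aim 1 as determining feasibility, acceptability and safety of a "multimodal prehabilitation intervention followed by a 4-6 week period of rehabilitation". The same section describes the intervention as remote exercise training "combined with nutritional support consisting of tailored nutritional advice, protein supplementation, and multivitamin and vitamin D supplements".

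Section 8.2.2 sets protein at 1.5 g/kg/day, or 1.2 g/kg/day in KDIGO categories G3a and G3b. Supplements for 3 to 4 weeks are handed out at T1, and a further six-week supply at discharge. Section 4.1 recognises a specific risk: "Renal function will be regularly monitored to ensure there is no adverse effect from the nutritional intervention".

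Section 13.0 defines the safety evaluation in two sentences. The first is "Safety will be evaluated by the number of adverse events (significant injury or medical event) during exercise". The second sets severity: the event leads the participant to a health professional, or it "limits their activities of daily living for at least two days".

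Outside Section 13.0, Section 9.0 has all adverse events reported under local requirements, and Section 14.4.1 lists an adverse events log among the stored data. Section 12.0 withdraws anyone who cannot continue either component and anticipates no research follow-up afterwards.

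**The concern.** The aim covers two components and the safety measure covers one. The contrast shows within Section 13.0 itself, where acceptability is measured separately for exercise and for nutrition but safety only for exercise.

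What is at stake is the meaning of the safety result. Section 4.2 makes the study's benefit conditional: "If a monitored prehabilitation program paired with nutrition support is found to be feasible, acceptable, and safe". Section 2.0 adds: "These findings are expected to inform the design of a larger multicenter trial". If Section 13.0 is followed exactly and no event occurs, a reader of the results could take the whole program as shown to be free of observed harm. The count behind that statement would hold no information on the supplements, which are the component with the named renal concern.

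**Working it through.** **Inputs.** Aim 1 and the components come from Section 3.0, the supplement supply from Section 8.2.2, the renal concern from Section 4.1, and the safety measure and severity definition from Section 13.0. The sample size of 24 is in Sections 3.0 and 5.1, and the surgical complication rate is in Section 2.0. The plan gives no safety rate, threshold or power figure, so there is nothing of its own to reproduce.

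**Step 1: apply the definition to example events.** To be counted, an event must occur during exercise and also meet the severity definition.

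| Hypothetical event | During exercise? | Meets severity? | In the safety result? |
|---|---|---|---|
| Fall in a tele-supervised session, seen by a clinician | Yes | Yes | Yes |
| Vomiting put down to the protein supplement, seen by a clinician | No | Yes | No |
| Decline in renal function found on monitoring, leading to medical review | No | Yes | No |
| Mild bloating, no care sought, daily activities unaffected | No | No | No |

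The second and third rows are the gap. They are as severe as the first row, by the plan's own standard, and are left out only because of when they occur. The severity sentence sets how serious an event must be; it does not widen the circumstances in which one counts.

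**Step 2: look for text that widens the result.** Section 9.0 concerns reporting to the institution and the IRB. Section 14.4.1 concerns where data are kept. Section 4.1 promises renal monitoring but no analysis of it. Section 13.0 does not refer to any of them. Nothing visible adds nutrition-related events to the safety evaluation.

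**Step 3: precision of an added count.** For zero participants with an event among n, the exact two-sided 95% upper limit is 1 − 0.025^(1/n). With n = 24 this is 1 − 0.85753 = 0.14247, or 14.2%. The Clopper-Pearson limits for 1/24 are 0.1% to 21.1%, and for 2/24 they are 1.0% to 27.0%. These figures describe what the added count could show; they do not measure the defect.

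**Step 4: why the added count should be split at surgery.** Section 2.0 states: "Veterans undergoing high-risk surgery have a 1 in 5 chance of suffering complications". If that rate applies here, the expected number with a complication is 24 × 0.2 = 4.8. Under Binomial(24, 0.2), P(2 to 9) = 0.954. An unsplit count would mix these events with any effect of the supplements.

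**Step 5: how long to count.** T4 is six weeks after surgery (Section 8.2.3), while the second six-week supply starts at discharge. Discharge comes after surgery, so a supply used in full lasts beyond T4 by the length of the post-operative stay. The count should end when supplements end, not at T4.

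**The case against.** The best defence is that nutrition harm is handled elsewhere. Advanced kidney disease is excluded, protein is reduced in G3a and G3b, nutrition experts adjust supplements after telephone check-ins, and inability to continue nutritional support leads to withdrawal. Nutrition adherence is an outcome, and the dropout questionnaire in Appendix 5 offers dislike of the supplements as a reason. In a single-arm pilot of 24, the practical loss is modest. All of this stands, and it limits the weight of the point. None of it changes what Section 13.0 calls the safety result.

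A reader might infer stronger claims that the documents do not support:

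- That nutrition-related events go unrecorded or unreported. Section 9.0 covers all adverse events and a log is kept.
- That the rehabilitation period is left out. The wording on exercise has no time limit and so also covers post-operative sessions; the gap is one of component.
- That renal monitoring lacks a schedule or action limits. The figure belonging to Appendix 3 is not shown, so no view of its content is possible.

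The opposite assumption, that every event needed is already logged, is not established either. Neither Section 9.0 nor Section 14.4.1 says what enters the log.

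**Conclusion.** The point holds as a mismatch between Aim 1 and its safety measure. Followed as written, Section 13.0 yields a result about exercise events and cannot answer the safety question for the nutrition component.

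The conclusion rests on reading the definition as worded and on the absence of any visible text that widens it. It needs no assumed rate. Only the surgical illustration does, since it takes the 1 in 5 complication rate to hold in this cohort. The documents give no non-surgical event rate, so the share of a combined count that would be surgical cannot be stated.

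The plan should be changed, but participant protection is not shown to fail. Even after the change, 24 patients allow only a description: zero participants with an event would still be compatible with a true proportion of up to 14.2%.

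**What to change.** In Section 13.0:

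1. Keep the count of adverse events during exercise.
2. Add a count of all adverse events meeting the existing severity definition, from T1 until supplements end or the participant withdraws. The investigator assigns each event to one class by most likely cause: exercise, nutrition, surgery or other. Show events before and after surgery separately. Give participants with an event over the number enrolled, with an exact 95% CI.
3. State the number withdrawn and the reasons, because Section 12.0 anticipates no research follow-up after withdrawal.
4. Where the monitoring promised in Section 4.1 yields renal values, summarise them descriptively and state how many participants have no repeat value. Do not attribute changes to protein, as there is no control arm.

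The cost is a few sentences and one table, with no change to sample size. The staff must also make sure that events outside exercise sessions are recorded until supplements end, which may be after T4. The drawbacks are that attribution is an unblinded judgement, intolerance below the severity threshold may not be captured, and events after withdrawal stay unobserved.

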## **14.0 Privacy, Confidentiality, and Information Security**

### **14.1 Lists of Data Reviewed and/or Collected for Screening/Recruitment and Conduction of Study:**

The Personal Health Information that will be obtained, used, and/or shared for this study includes:

Identifier(s)	Source(s) of Health Information
 Names	 Medical history & physical exam information

Identifier(s)	Source(s) of Health Information
 All geographic subdivisions smaller than a State, including street address, city, county, precinct, and zip code. Describe: street address, city, state, zip code for mailing participant payments	 Photographs, videotapes, audiotapes, or digital or other images
 All elements of dates (except year) for dates directly related to an individual, including birth date, admission date, discharge date, visit or treatment dates, etc.; and all ages over 89, Describe: Date of preop evaluation/POSH appt.; dates of postop appointments; date of surgery; dates of laboratory test results; date of birth	 Biologic specimens (e.g., blood, tissue, urine, saliva). Describe:
 Telephone numbers	 Progress notes
 Fax numbers	 Diagnostic / Laboratory test results
 Electronic mail addresses	 Operative reports
 Social Security Numbers	 Imaging (x-ray, CT, MRI, etc.)
 Medical record numbers	 Discharge summaries
 Health plan beneficiary numbers	 Survey / Questionnaire responses
 Account numbers	 Billing records
 Certificate and/or license numbers	 HIV testing or infection records
 Vehicle identifiers and serial numbers, including license plate numbers	 Sickle cell anemia information
 Device identifiers and serial numbers	 Alcoholism or alcohol use information
 Web Universal Resource Locators (URLs)	 Drug abuse information
 Internet Protocol (IP) address numbers	 Mental health (not psychotherapy) notes
 Biometric identifiers, including finger & voice prints	 Psychological test results
 Full-face photographic images and any comparable images	 Genetic testing
 Any other unique identifying number, characteristic, or code, describe: Patient address including latitude/longitude and rural/suburban/urban designation.	 Other, describe:
*Note: This is not the unique code assigned to otherwise de-identified health information for re-identification purposes.	

All non-Veterans enrolled in this study will receive the VA Notice of Privacy Practices (NOPP) and are requested to sign the acknowledgment form. The signed acknowledgment form will be maintained with the research records.

#### 14.2 Data and/or Specimen Acquisition:

Data for this study will be collected through (*check all that apply*):

- Prospective data and/or specimen collection obtained from participants. Provide description of processes: Assessments of physical function, mobility, nutrition,

anxiety/depression, and health-related quality of life will be collected. Data from the medical record will also be accessed and used.

iPad devices will be issued to relevant participants and become their property. There will be no research data stored on these devices – they are used solely for communicating with study team members regarding appointments and food diaries, as well as participating in exercise sessions.

Retrospective data collection and/or specimens obtained from medical chart review/data access. Describe how data will be obtained (e.g., fileman, CDW, etc.):

Retrospective data collection and/or specimens obtained from an IRB-approved data and/or specimen repository. Indicate the repository source including name, VA location, and IRB number:

*Note: for data and/or specimens obtained from a VA approved data repository, a Data Use Agreement (DUA) must be executed prior to obtaining data and/or specimens. See VHA Handbook 1200.12 for further information.*

#### **14.3 Level of Data:**

The following level(s) of data will be acquired/maintained for this study (*check all that apply*):

Identifiable—Data contains direct identifiers.

Coded—Data linked to a specific by a code rather than a direct identifier for re-identification purposes. Only someone possessing the key to the code can link the data to a particular participant.

De-Identified (all 18 HIPAA identifiers removed

- Verified Statistically
- OR
- Verified by Absence or Removal of 18 HIPAA identifiers

Limited Data Set

Other: Describe:

#### **14.4 Location of Data and/or Specimens, and Data Retention Plan**

##### **14.4.1 Data and/or Specimen Location**

Hardcopy documents, including surveys, ICFs and HIPAA Forms, will be stored in folders and binders and kept inside a locked cabinet in our Anesthesia Research Office (C3011A).

Data will be stored electronically on secure VA servers accessible only to study personnel through VA workstations—file path S:\Anesthesia Research\[name]\PREVENT\Data. Data that will be stored electronically include screening and enrollment logs, adverse events log, and data sets related to functional and nutritional assessments.

There will be no research-related data stored on the iPad tablet devices.

Paper records of data include ICFs, HIPAA Forms, and assessments on function and nutrition and will be stored inside locked cabinets in our research office.

Specimens will not be collected for this research project.

Data will be also be placed at the VA Informatics and Computing Interface (VINCI; <http://vaww.vinci.med.va.gov/vincicentral/VINCIWorkspace.aspx>). The VA Informatics and Computing Infrastructure is a partnership between the VA Office of Information Technology and the Veterans' Health Administration Office of Research and Development. Researchers and operations staff can use VINCI to access data and statistical analysis tools in a virtual working environment through a certified VHA network computer using the VA Intranet or Virtual Private Network (VPN).

#### **14.4.2 Data Retention Plan**

Research records will be maintained and destroyed according to the National Archives and Records Administration, Records Schedule Number: DAA-0015-2015-0004. Records destruction, when authorized, will be accomplished using the then current requirements for the secure disposal of paper and electronic records. Currently, destruction of research records (see DAA-0015-2015-0004, section 7.6 "Research Investigator Files" for materials included in research records) is scheduled for 6 years after the cut-off (the cut-off is the completion of the research project) and may be retained longer if required by other federal agencies. Records will not be destroyed without pre-notification to the facility records manager.

Other data retention plan, describe:

